8.7. Dose Modifications

Dose reductions and interruptions will be summarized for subjects who had at least one dose reduction or interruption. In addition, summary statistics (frequency of patients and median number of days) will be produced for time to first dose reduction/interruption as well as the number of reduction/interruptions per subject.

10. STATISTICAL ANALYSIS OF EFFICACY ENDPOINTS

All efficacy analyses will be performed using the ITT population and the EE population. The ITT population shall form the primary analysis while the EE population shall form the sensitivity analysis of the endpoints.

10.1.1. Overall Response Rate

Under the IMWG uniform response criteria, a response is defined as being either a stringent complete response (sCR), complete response (CR), very good partial response (VGPR) or a partial response (PR). Investigator's assessment of response will be used for the response analysis. The overall response rate (ORR) is defined as the percentage of subjects with a confirmed disease response (sCR, CR, VGPR, or PR) according to the International Myeloma Working Group International Myeloma Working Group International Myeloma Working Group (IMWG) uniform response criteria, over the number of subjects included in the analysis. For the response to be confirmed, a consecutive disease assessment must achieve the same response or better. Confirmed responses that are documented after the initiation of another anti-myeloma treatment will not be counted as responses. Subjects without a disease assessment will be considered a non-responder for the purpose of the ORR. The ORR shall be presented along with the corresponding Clopper-Pearson 95% confidence interval (CI).

The proportion of subjects in each response category [i.e. sCR, CR, VGPR, PR, stable disease (SD), PD, relapse, relapse from CR, and Not Evaluable] as well as the proportion of subjects without any disease assessment will be calculated.

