3.5. Sample Size

Approximately 720 subjects across twenty-one European countries will be enrolled into this study. This sample size has been determined to enable the characterisation of currently infrequent AEs. As such, a sample size of 720 subjects will allow detection of any infrequent AE, defined as an AE with a frequency of 0.4% (3/720), assuming a study power of 95%. Under this calculation, an infrequent event with a frequency of 0.4% will be confirmed if at least 1 of 720 evaluable subjects experiences such an event.

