10.1.2. Time to Response

TTR is calculated as the time from study enrollment, defined as the IVRS enrollment date, until a documented disease response (either SCR, CR, VGPR or PR). Subjects not observed with a response will not be included in the analysis. The analysis will consist of presenting the number of subjects available for analysis of TTR, the mean and median time as well as the minimum and maximum time to reach a response.

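### ORR confirmation rule: on the usual reading, a response that falls in category at every visit (VGPR, PR, PD) is never confirmed, although PR, PR, PD is

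*SAP*

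**What the plan says.** SAP section 10.1.1 states that "a response is defined as being either a stringent complete response (sCR), complete response (CR), very good partial response (VGPR) or a partial response (PR"). The ORR is the "percentage of subjects with a confirmed disease response (sCR, CR, VGPR, or PR") among the subjects analysed. Confirmation has one rule: "For the response to be confirmed, a consecutive disease assessment must achieve the same response or better". A confirmed response recorded after another anti-myeloma treatment has begun is not counted.

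The only explicit non-responder rule is "Subjects without a disease assessment will be considered a non-responder for the purpose of the ORR". Nothing in the section says what happens when one response category is followed by a lower one that is still a response. On precision, "The ORR shall be presented along with the corresponding Clopper-Pearson 95% confidence interval (CI").

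The neighbouring endpoints are worded differently. TTR (section 10.1.2) runs from enrollment "until a documented disease response (either SCR, CR, VGPR or PR"). DoR (section 10.1.3.1) likewise starts at the first response on record. Neither mentions confirmation.

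**The concern.** The ORR is a yes/no endpoint: did the subject reach PR or better, and was this confirmed? The phrase "For the response to be confirmed, a consecutive disease assessment must achieve the same response or better" works at the level of the individual category, because a better response exists only if the categories are ranked. Applied visit by visit in forward order, the rule asks each response to be matched or exceeded at the following assessment. A subject who starts deeper and then declines can fail this at every step while being in response at consecutive visits.

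Two things are at stake. First, a subject can be scored a non-responder although another subject, who did no better at any visit, is scored a responder. Second, the subject lost from the ORR may still enter TTR and DoR, since those sections do not require confirmation. Responder counts might then disagree between Tables 14.2.1.1, 14.2.2 and 14.2.3 listed in Appendix B.

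**Working it through.** The SAP states no expected ORR, no precision target for ORR and no frequency of falling responses, so there is no figure of its own to reproduce. The check is of the rule's logic, followed by an illustration of size.

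**Inputs.** Response categories and the confirmation rule: section 10.1.1. Ranking PD < SD < PR < VGPR < CR < sCR: implied by the words about a better response. N = 720: section 3.5 ("Approximately 720 subjects across twenty-one European countries will be enrolled into this study"), used only for scale. ORR of 25–40% and the share of subjects affected: assumptions.

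**Step 1: named sequences.** *Forward*: a response is confirmed if the next assessment ranks at least as high. *Either side*: the adjacent earlier assessment may also confirm.

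| Sequence | Forward | Either side |
|---|---|---|
| PR, PR, PD | confirmed | confirmed |
| VGPR, PR, PD | not confirmed | confirmed |
| CR, VGPR, PD | not confirmed | confirmed |
| CR, VGPR, PR, PD | not confirmed | confirmed |
| VGPR, PR, PR | confirmed | confirmed |
| PR, VGPR, PR, PD | confirmed | confirmed |

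The first two rows show the inconsistency. VGPR, PR, PD is at least as good as PR, PR, PD at every visit and better at one, yet only the latter counts on the forward reading. The last two rows show the limit: one pair at the same or a better category anywhere in the sequence is enough.

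**Step 2: all patterns.** Take every sequence of 2, 3 or 4 assessments in which PD can occur only at the last, and keep those with two consecutive assessments of PR or better. The forward reading rejects 6 of 16, 22 of 112 and 91 of 656 respectively. For length 2 this is easy to verify: 4 × 4 = 16 pairs of response categories, of which 4 × 3 / 2 = 6 fall. The either-side reading rejects none. These are counts of possible patterns, not probabilities.

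**Step 3: size, under assumptions.** If 0.5–2% of 720 subjects were affected:

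- 0.005 × 720 = 3.6, so about 4 subjects; 4/720 = 0.56 points.
- 0.02 × 720 = 14.4, so about 14 subjects; 14/720 = 1.94 points.

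The Clopper-Pearson limits for x responders of n are the 2.5% quantile of Beta(x, n − x + 1) and the 97.5% quantile of Beta(x + 1, n − x). At n = 720 the half-widths are 3.23, 3.41, 3.55 and 3.64 points for an ORR of 25, 30, 35 and 40%.

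**Step 4: a wider range.** Express the affected group as a share of responders instead. With 216/720 = 30.0% (95% CI 26.7–33.5) and 5% of responders affected, 205/720 = 28.5% (25.2–31.9) remain, a loss of 1.5 points. Over assumed ORRs of 20–40% and shares of 1–10%, the loss runs from 1/720 = 0.1 points to 29/720 = 4.0 points. Only towards the upper end does it reach the half-width.

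**The case against.** The strongest reply is that the SAP asks for a consecutive assessment, not the next one. In VGPR, PR, PD the VGPR visit is adjacent to the PR visit and better than it, so the PR can be said to meet the rule as written. This stands as a possible reading, and on it no sequence is lost. But the SAP does not state it, and confirmation is usually taken to come from the following assessment. Two programmers could therefore derive different ORRs from the same data, which is itself a reason to fix the sentence.

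A second reply is that confirmation at category level may be a deliberate, conservative choice. The SAP indeed gives no other definition of confirmation against which to call the rule wrong. The point does not need one: it rests on the rule ranking VGPR, PR, PD below PR, PR, PD, which a conservative choice does not explain.

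Third, little depends on it. ORR is a secondary endpoint in a single-arm safety study, no formal hypothesis testing is planned (section 4.1.4), and the sample size was set for adverse-event detection. This stands and limits the weight of the point.

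A reader might go further in three ways that the document does not support. One is that waning responders in general are lost, and that they are common in refractory disease: the SAP gives no frequency, and with assessments on Day 1 of each 28-day cycle (section 3.1) a subject must lose a category at each visit throughout every run of responses. Another is that these subjects drop out of the response-category table: section 10.1.1 does not limit that table to confirmed responses, so a change of category there is possible but not established. The third is that the ORR is certainly biased: that holds only on the forward reading and only if such subjects occur.

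**Conclusion.** The point holds in a limited form. On the usual reading, section 10.1.1 leaves a subject whose responses fall in category at every step without a confirmed response, although PR, PR, PD counts. On the other tenable reading nobody is lost. The ORR therefore depends on an interpretation that the SAP does not fix.

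The direction is certain: compared with counting any two consecutive responses, the forward reading can only lower the ORR. The size is not known. The estimate of about 0.6–1.9 points rests on an assumed 0.5–2% of subjects and is smaller than the interval half-width at an assumed ORR of 25–40%. The effect is probably small and touches a descriptive secondary endpoint. The rule should be corrected because it is incoherent and cheap to repair, not because a study conclusion is shown to change.

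**What to change.** Replace the confirmation sentence in section 10.1.1 with: *A response is confirmed when two consecutive assessments before any new anti-myeloma treatment are both PR or better, in either order; the confirmed category is the lower of the two.* Under this wording VGPR, PR, PD is a confirmed PR and CR, VGPR, PD a confirmed VGPR.

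State in sections 10.1.2 and 10.1.3.1 whether TTR and DoR use the same confirmed responders, so that the counts agree across the three endpoints. It would also help to say whether the response-category table shows confirmed responses.

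The cost is one reworded sentence, short clarifications and one changed derivation. No new data are needed.

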10.1.2. Time to Response

TTR is calculated as the time from study enrollment, defined as the IVRS enrollment date, until a documented disease response (either SCR, CR, VGPR or PR). Subjects not observed with a response will not be included in the analysis. The analysis will consist of presenting the number of subjects available for analysis of TTR, the mean and median time as well as the minimum and maximum time to reach a response.

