10.1.3.1. Duration of Response

Duration of response is defined as the time from the first documented disease response to the IP (either SCR, CR, VGPR or PR) until the first recorded disease progression on the IMWG assessment of response CRF or LTFU CRF, whichever occurs first, or death if no disease progression recorded (refer to PFS for complete event details) for responders.

Censoring of subjects not experiencing an event are similar to PFS outlined in Table 1 with the following exceptions:

- If a subject is still on therapy and therefore has no LTFU CRFs, then censor at time of last response assessment, otherwise,
- If the subject did not have a disease progression during therapy but has entered into long term follow-up and still no disease progression is indicated, then censor at the time of the last completed LTFU CRF.

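### TTR is not restricted to the confirmed responders counted in ORR, and the SAP leaves open which responders and which response date DoR uses

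*SAP*

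**What the plan says.** **ORR (SAP 10.1.1).** The section opens with a general definition in which "a response is defined as being either a stringent complete response (sCR), complete response (CR", VGPR or PR; confirmation is not mentioned there. It then defines ORR as the "percentage of subjects with a confirmed disease response (sCR, CR, VGPR, or PR" under the IMWG criteria. The confirmation rule follows: "For the response to be confirmed, a consecutive disease assessment must achieve the same response or better". A second condition is added: "Confirmed responses that are documented after the initiation of another anti-myeloma treatment will not be counted as responses".

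**TTR (SAP 10.1.2).** Time runs from the IVRS enrollment date "until a documented disease response (either SCR, CR, VGPR or PR"). The only exclusion is this: "Subjects not observed with a response will not be included in the analysis". The output is the number of subjects, mean, median, minimum and maximum.

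**DoR (SAP 10.1.3.1).** DoR is "the time from the first documented disease response to the IP (either SCR, CR, VGPR or PR") up to progression or death, and is restricted to responders. The SAP does not define that word. It is analysed by Kaplan-Meier (SAP 10.1.3).

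**The concern.** The SAP speaks of confirmed responses for one endpoint and documented responses for the other two, and no sentence says that the TTR and DoR subjects are the ORR responders. Two programmers could follow the text faithfully and deliver different subject counts and different times.

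Readers take ORR, TTR and DoR as three descriptions of the same patients. Here Tables 14.2.1.1, 14.2.2 and 14.2.3 could carry different responder counts with nothing to explain why. The same endpoints are also listed as inputs to the exposure-response analysis (SAP 13).

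The timing of the first full analysis makes this more than theoretical. Under SAP 3.1 it takes place once all enrolled subjects have completed up to 2 cycles, with response assessed on Day 1 of each cycle. A late enrollee whose first PR falls at the most recent assessment cannot yet have been confirmed. That subject is outside the ORR numerator but inside TTR as written.

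**Working it through.** **1. The plan's own figure.** The only sizing figure concerns adverse events (SAP 3.5). With p = 3/720, 1 − (1 − 3/720)^720 = 95.05%, against the stated 95%. It reproduces and does not depend on response, so nothing here changes N = 720.

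**2. The definitions side by side.**

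| | ORR (10.1.1) | TTR (10.1.2) | DoR (10.1.3.1) |
|---|---|---|---|
| Confirmation required | yes | not stated | not stated |
| Responses after new therapy excluded | yes | not stated | only hinted at, by tying response to the IP |
| Who is analysed | all subjects in the population | subjects with an observed response | responders (undefined) |
| Response date | not needed | a documented response | first documented response |

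Every ORR responder has a documented response, so the TTR set as written contains the ORR responders and possibly others. The DoR set is either the ORR responders or all documented responders.

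**3. Two subjects under the 28-day schedule** (visit windows ignored; months = days/30.4167, SAP 4.1.2).
- *PR, then PD at the next visit.* ORR: non-responder. TTR: included. DoR: excluded on one reading; on the other, an event at about 28 days, 28/30.4167 = 0.9 months.
- *PR, SD, PR, PR.* ORR: responder, through the second PR, which the third confirms. The first documented PR is two visits before the confirmed one. Starting there makes TTR shorter and DoR longer by 56 days, 56/30.4167 = 1.8 months. This ambiguity remains even if DoR is confined to confirmed responders.

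**4. How many extra subjects TTR could carry.** The SAP gives no response rate or unconfirmed share, so both are assumed. With c confirmed responders among 720 and a share u of all documented responders unconfirmed, the documented set is c/(1 − u).

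| Assumed confirmed ORR | c | u = 5% | u = 10% | u = 20% |
|---|---|---|---|---|
| 20% | 144 | 152 (+8) | 160 (+16) | 180 (+36) |
| 30% | 216 | 227 (+11) | 240 (+24) | 270 (+54) |
| 40% | 288 | 303 (+15) | 320 (+32) | 360 (+72) |

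**5. Median DoR, only if unconfirmed responders enter and all fail early.** Assume exponential durations with median m in confirmed responders and k = 1 or 2 months in the others. The pooled median t solves (1 − u)·0.5^(t/m) + u·0.5^(t/k) = 0.5.

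| Assumed m (months) | u = 5% | u = 10% | u = 20% |
|---|---|---|---|
| 6 | 5.57 to 5.68 | 5.14 to 5.36 | 4.25 to 4.76 |
| 8 | 7.41 to 7.49 | 6.80 to 6.99 | 5.53 to 6.01 |
| 10 | 9.26 to 9.32 | 8.49 to 8.63 | 6.83 to 7.26 |

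The falls run from 6 − 5.68 = 0.3 to 10 − 6.83 = 3.2 months. If instead the unconfirmed responders had the same duration distribution as the confirmed ones (k = m), the equation gives t = m and no fall at all.

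**The case against.** A reader might infer that the three endpoints use three different responder sets, and that DoR is in fact diluted by one-off responses and biased short. The text does not support that. TTR and DoR share the documented-response wording, so there are at most two sets. DoR is expressly limited to responders, and the only place where the SAP sorts subjects into responders and non-responders is the ORR section, where confirmation applies. On that natural reading, the first documented response fixes only the start date, and no one-off responder enters. DoR is also tied to response to the IP, which points towards excluding responses on later therapy. Mixing is therefore a permitted reading, not a stated rule.

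The early-failure model is also severe. Under SAP 10.1.3, SD is not progression, so a single PR followed by SD keeps accruing DoR, and a subject whose lone PR is the last assessment before cut-off is censored. Only PR followed directly by PD fits.

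Three further points limit the matter. Responses after new therapy will be few, because scheduled efficacy assessment ends within 28 days of IP discontinuation (SAP 3.1). TTR reports its own subject count, so a mismatch would be visible. And the CRF, which is not shown, might record PR only once confirmed.

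All of this stands as a limit on size, but it does not close the gap. Section 10.1.2 has no restriction to responders. The non-responder wording in 10.1.1 is confined to the purpose of ORR, and that section's opening definition of response omits confirmation. A visible mismatch is still an unexplained one. And if the CRF held only confirmed responses, the confirmation rule in 10.1.1 would have little to do.

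**Conclusion.** The point holds for TTR on the plain wording: its analysis set can include subjects who are ORR non-responders. For DoR it holds as an ambiguity. The SAP does not settle whether unconfirmed responders enter or, for confirmed responders, whether the clock may start at an earlier unconfirmed response.

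The size cannot be derived from the SAP. The 8 to 72 extra TTR subjects rest on assumed response rates and unconfirmed shares. The 0.3 to 3.2 month fall in median DoR rests in addition on unconfirmed responders being admitted and all failing early, so it is an upper bound under those assumptions rather than an expected effect. Even the direction is open: PR followed at once by PD shortens the median, PR followed by SD need not, and an early start date lengthens DoR.

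These are descriptive secondary endpoints in a single-arm study with no formal testing planned. The primary safety endpoint is untouched. The correction is still worth making, because it determines reported counts and times and costs almost nothing.

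**What to change.** State in both 10.1.2 and 10.1.3.1:

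> TTR and DoR are computed in the subjects counted as responders for ORR. The response date is the first documentation of PR or better that is subsequently confirmed and that precedes any new anti-myeloma therapy.

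This settles membership, start date and the new-therapy exclusion together. If the sponsor does want unconfirmed responses in TTR or DoR, the SAP should say so and report both sets.

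The cost is this short statement in two sections and one flag in the response dataset. The downside is a slightly smaller N for TTR and possibly for DoR. At the first full analysis, subjects whose response is not yet confirmed will be absent from all three endpoints and can enter at the final update.

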10.1.3. Time to Event Analyses

Four time to event endpoints (DoR, TTP, PFS, and OS) will be analysed for this study. Response values (as determined by the site investigator based on the IMWG uniform response criteria) categorised as PD, relapse and relapse after CR indicate that the subject had a disease progression, while other response values (i.e. sCR, CR, VGPR, PR and SD) indicate that the subject did not have a disease progression.

For each time to event endpoint, the Kaplan-Meier method will be used to estimate the survival distribution function. The median, 25 and 75 percentile of the survival distribution along with

the two-sided 95% CI for the median will be estimated. In addition, the event rates at 6, 12 and 24 month time-points will be computed, along with the standard errors. The plots of survival curves using Kaplan-Meier estimates will be presented as appropriate.

10.1.3.1. Duration of Response

Duration of response is defined as the time from the first documented disease response to the IP (either SCR, CR, VGPR or PR) until the first recorded disease progression on the IMWG assessment of response CRF or LTFU CRF, whichever occurs first, or death if no disease progression recorded (refer to PFS for complete event details) for responders.

Censoring of subjects not experiencing an event are similar to PFS outlined in Table 1 with the following exceptions:

- If a subject is still on therapy and therefore has no LTFU CRFs, then censor at time of last response assessment, otherwise,
- If the subject did not have a disease progression during therapy but has entered into long term follow-up and still no disease progression is indicated, then censor at the time of the last completed LTFU CRF.

10.1.3.2. Progression-Free Survival

Progression Free Survival is calculated as the time from study enrollment, defined as the IVRS enrollment date, until either PD or death (any cause). Subjects without an event (either a documented PD or death) at the time of study end will be censored at the time of their last documented disease assessment or at the IVRS enrollment date if no disease assessment was conducted. A subject with a documented PD directly following a missing assessment, if not having previously had a documented PD, will be censored at the time of the assessment directly preceding the missing assessment.

Missing assessments are defined as 2 or more consecutive missing assessments, considered as > 66 days (during the treatment period) or > 192 days (during the long-term follow-up phase) between the last adequate assessment and the date of the event, or, >94 days if there is no assessment after enrollment and the subject having an event.

Table 1 below includes the event and censoring rules for PFS.

Table 1: Event and Censoring Rules for Progression Free Survival

Scenario	Date Subject has Event or is Censored	Comment
Progression documented at scheduled assessment	EMA and FDA Guidelines: Event date = first disease assessment date where a PD is documented	A subject with a documented PD directly following a missing assessment, if having not

Scenario	Date Subject has Event or is Censored	Comment
		had a PD observed previously, shall be censored at the time of the last documented assessment or the IVRS enrollment date if there is no prior response assessment.
Progression documented between scheduled assessment	EMA Guidelines: Event = date of documented progression. FDA Guidelines: Event data = last scheduled adequate assessment prior to the unscheduled assessment; if no adequate assessment at scheduled visits existed prior to the unscheduled assessment, then event date = date of unscheduled assessment.	
Subject did not progress nor die	EMA and FDA Guidelines: Censored date: date of last adequate assessment without PD; if no adequate assessment existed then censored at date of enrollment.	
Subject died without initial documented progression	EMA and FDA Guidelines: Event date = date of death.	Per FDA Guidelines if the death date is after AMT then the patient is censored at the last assessment date.

For events during the treatment period: Death or progression from the follow-up within 2 cycles (2 x 28 +10-day window = 66 days) after the latest of: treatment period discontinuation date, last cycle end date of study drug, and last adequate assessment date during treatment period
 
For events during the long-term follow-up phase: Death or progression within 6 months (6 x 30.25 + 10-day window = 192 days) after the last assessment
	EMA and FDA Guidelines: Event date = date of death or documented progression if occurring before death.	

Scenario	Date Subject has Event or is Censored	Comment

For treatment period: Death or progression from the follow-up more than 2 assessment cycles (2 x 28 +10-day window = 66 days) after the latest of: treatment period discontinuation date, last cycle end date of study drug, and last adequate assessment date during treatment period
 
For long-term follow-up phase: Death or progression from the follow-up more than 2 assessment cycles, i.e. 6 months (6 x 30.25 + 10-day window = 192 days) after the last assessment
	
EMA and FDA Guidelines: Censor date = date of last adequate assessment with evidence of no progression; if no adequate assessment existed then censor at date of enrollment.
	

New anti-myeloma/non-protocol treatment started prior to progression/death
	
EMA Guidelines: Event date = date of documented progression/death.
 
FDA Guidelines: Censor date = date of last adequate assessment with evidence of no progression; if no adequate assessment exists then censor at the date of enrollment.
	

Death or progression during the treatment period after an extended lost-to-follow-up time (two or more missed scheduled assessments)
	
EMA Guidelines: Event date = date of documented progression or death.
 
FDA Guidelines: Censor date = date of last adequate assessment with evidence of no progression; if no adequate assessment exists then censor at the date of enrollment.
	

Abbreviations: CR = complete response; DoR = Duration of response; OS = overall survival; PD = Disease progression; PFS = Progression free survival; PR = Partial response; sCR = stringent complete response; TTP = Time to progression; VGPR = very good partial response.

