Efficacy measurements shall be collected during the Screening period, at Day 1 (± 1 day) of each cycle and within 28 days post IP discontinuation, with the exception of response assessments which will not be collected during the Screening period. Survival status and recording of subsequent anti-myeloma regimens will be recorded within 28 days post IP discontinuation and during the Follow-up period every 3 months (84 ± 14 days).

Note that the visit (or assessment) occurring just prior to initiation of the IP is defined as “baseline” (i.e., Day 1 of Cycle 1). However, data from the Screening period will be substituted for a given measure if data at Day 1 Cycle 1 is not available.

Dose modifications and interruptions of the IP are permitted throughout the study.

Subjects will remain on study until a specific event, including, but not limited to, becoming lost-to-follow-up, death and withdrawal of consent.

The first full analysis of the primary and secondary endpoint will be conducted once all enrolled subjects have completed up to 2 cycles of the IP if having not stopped therapy earlier.

A final, updated, analysis will be conducted at the time of study close, the point when all subjects will have discontinued from the study, i.e. 5 years from the last issued IVRS enrollment date if having not discontinued from the study before this point.

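### PFS Table 1: the 66-day censoring clause reaches into follow-up, where the only stated interval is 84 ± 14 days, and it overlaps the 192-day clause with no rule on which prevails

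*SAP*

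**What the plan says.** Section 10.1.3.2 reserves this kind of censoring for gaps in assessment: "Missing assessments are defined as 2 or more consecutive missing assessments, considered as > 66 days (during the treatment period" is the definition on treatment, and "> 192 days (during the long-term follow-up phase) between the last adequate assessment and the date of the event" is its counterpart in follow-up.

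Table 1 turns this into two censoring clauses in one cell. The clause headed for the treatment period reads "Death or progression from the follow-up more than 2 assessment cycles (2 x 28 +10-day window = 66 days) after the latest of", and the anchor dates are "treatment period discontinuation date, last cycle end date of study drug, and last adequate assessment date during treatment period". The clause for the long-term follow-up phase applies to events "more than 2 assessment cycles, i.e. 6 months (6 x 30.25 + 10-day window = 192 days) after the last assessment". Under both sets of guidelines the consequence is the same: "Censor date = date of last adequate assessment with evidence of no progression; if no adequate assessment existed then censor at date of enrollment". The row above mirrors these limits and makes events inside them count.

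Section 3.1 starts the Follow-up period at permanent discontinuation of IP. It plans an efficacy assessment within 28 days of stopping. Survival status and later myeloma regimens are then recorded "during the Follow-up period every 3 months (84 ± 14 days").

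**The concern.** The 66-day limit follows the on-treatment rhythm, but the clause that uses it covers deaths and progressions found in follow-up. Contacts there are about three months apart. A subject who stops IP without progression, misses nothing and is found to have progressed at the first three-monthly visit can fall outside 66 days. The event is then removed and follow-up is cut back to the last clean assessment. The same progression satisfies the 192-day event clause, so two programmers could each follow Table 1 and reach opposite results.

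The subjects exposed are those who stopped for reasons other than progression, such as an adverse event. Censoring them is plausibly informative and would lengthen PFS. The EMA and FDA PFS tables (14.2.5.1 and 14.2.5.2) share this row, so neither checks the other. DoR and TTP refer to PFS for their event details.

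**Working it through.** **The plan's own limits.** On treatment: 2 × 28 + 10 = 66 days. Long-term follow-up: 6 × 30.25 + 10 = 191.5, rounded to 192 days. Both reproduce.

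**The on-time window.** 84 − 14 = 70 and 84 + 14 = 98, so a punctual visit falls on one of 29 days (70 to 98). Even the earliest exceeds 66.

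**What the 66-day clause can act on.** Its anchor is the latest of three dates that include discontinuation, so it is never earlier than discontinuation. Follow-up begins at discontinuation. Any event more than 66 days after the anchor therefore lies in follow-up, and the clause can only remove post-treatment events.

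**How much of the window is lost.** Let day 0 be discontinuation, *a* the anchor day and *v* the day of the first follow-up visit. The event is censored if *v* − *a* > 66. The SAP does not say whether the visit within 28 days of stopping is a treatment-period assessment (which would move *a*), nor from when the 84 days run. Taking that visit on day 28 where it matters:

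| Anchor *a* | 84 days run from | Gap *v* − *a* (days) | Censored at 66 | Censored at 192 |
|---|---|---|---|---|
| Day 0 | Day 0 | 70 to 98 | 29 of 29 | 0 |
| Day 0 | Day 28 | 98 to 126 | 29 of 29 | 0 |
| Day 28 | Day 28 | 70 to 98 | 29 of 29 | 0 |
| Day 28 | Day 0 | 42 to 70 | 4 of 29 | 0 |

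In the last line the limit reaches day 28 + 66 = 94, so only days 95 to 98 are censored. A visit on exactly day 84 has a gap of 84 − 28 = 56 and is an event. If the earlier visit falls sooner, the loss grows: the day-84 visit is censored when *a* ≤ 17 (84 − 17 = 67), and the whole window when *a* ≤ 3 (70 − 3 = 67).

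Deaths follow the same arithmetic. A death on day 80 is censored with the anchor at day 0 (80 > 66) and counts with the anchor at day 28 (80 − 28 = 52).

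**Effect on PFS.** The SAP gives no inputs, so these are assumptions: median time to progression or death 3 to 6 months, 20 to 40% of subjects stopping IP without an event, 15% of events being deaths, and the first follow-up visit 84 ± 14 days after stopping. Simulation of the 66-day against the 192-day limit gives:

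- clock at discontinuation: about 4 to 13% of subjects lose an event, and 6-month PFS is about 1 to 4 points higher (for example 30% becomes 34%);
- clock restarted at the visit within 28 days: about 2 to 9% of subjects, and about 1 to 2 points;
- 192-day clause governing: no subjects, and no change.

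**The case against.** The strongest reply is that the limits are split by phase, in the text and in Table 1. A progression on day 84 after stopping occurs in follow-up, so the 192-day limit applies and nothing is lost. This shows that a benign reading exists, but it does not settle the matter: it would leave the 66-day censoring clause with nothing to censor, although that clause expressly covers follow-up events.

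Second, the 66 days run from the latest of three dates, and a visit within 28 days of stopping may move the anchor. That stands. With the visit on day 28 and the 84 days counted from discontinuation, most punctual visits are events.

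Third, 84 ± 14 days is stated for survival status and subsequent therapy, not for disease assessment. That also stands. Its use for progression is inferred from Table 1 equating two follow-up assessment cycles with six months, and from DoR and TTP taking progression from the long-term follow-up form. The SAP states no shorter interval for progression in follow-up.

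A reader might infer that every on-time progression at the first follow-up visit is censored and that PFS is therefore biased upwards. The documents do not support that, because the 192-day clause can be read to keep the event and the anchor and the start of the 84 days are both open. The simulated sizes also rest on inputs that are not in the SAP.

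**Conclusion.** The point holds as a defect in the stated rule. Read literally, one Table 1 clause can censor an event at an on-time first follow-up visit. That runs against the SAP's own principle of censoring only after two or more consecutive missing assessments. Another clause in the same cell makes that event count, and nothing says which prevails. The reach is 29, 4 or 0 of the 29 window days in the cases worked through, and an early visit after stopping gives values in between. The effect on 6-month PFS runs from zero to a few percentage points, under assumed inputs and with the three-monthly interval inferred for progression.

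It should be fixed, but it does not threaten the study's main conclusion. PFS, TTP and DoR are secondary endpoints in a single-arm safety study with no formal hypothesis testing planned, and OS does not use these rules.

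**What to change.** In section 10.1.3.2 and Table 1:

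- Confine the 66-day limit to events while the subject is still in 28-day cycles, by removing the reference to follow-up from both treatment-period clauses (the event row and the censoring row). The anchor must then be the last adequate assessment, since an on-treatment event cannot fall after a date that is at or beyond discontinuation. Reconcile the result with the last row of Table 1, which keeps on-treatment events after two or more missed assessments under the EMA rules.
- State that any progression or death after IP discontinuation is judged by the plan's own 192-day limit, counted from the last adequate assessment. The longest on-time gap above is 28 + 98 = 126 days, so no punctual first visit is lost.
- Say whether the visit within 28 days of stopping belongs to the treatment period or to follow-up, and from when the 84 days run.
- Apply the same rule to the DoR and TTP event definitions.

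The cost is SAP wording and one programming condition, with no new data. PFS may come out slightly shorter. A few events would also count after two missed assessments: a subject last assessed at discontinuation who misses the visit within 28 days and the day-84 visit, and progresses on day 168, is inside 192 days. The SAP should accept that openly or add a condition for it.
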